5.4 Additional consent

The ICF contains optional additional statements for the participant to:

- Agree for any remaining blood samples to be stored beyond the end of the trial to be used in future research which conforms to all relevant legal, governance and ethical requirements.
- Agree to be contacted by a researcher to discuss taking part in a research interview.
- Agree for their anonymised data from the trial to be shared with other Universities/third parties for research purposes.

• Agree to take part in the detailed mechanistic study (if the recruiting site is selected to recruit participants to the sub-study). See Section 0 for further details.

6. ENROLMENT AND RANDOMISATION

6.1 Identification

Patients will be identified by site PIs, or delegated individuals at that site, in conjunction with routine care teams. Patients may be identified by participating sites in any reasonable way for their practice/hospital and either invited directly or using the invitation letter. We anticipate primary care staff searching databases using search protocols developed by the lead Clinical Research Network, and inviting potential participants based on eligibility at this pre-screening stage (age \geq 18 years, primary clinical diagnosis of COPD and ≥ 2 acute exacerbations of chronic obstructive pulmonary disease (AECOPD) in the last 12 months). Searches of pre-existing, research databases, and prospective identification of patients in clinics may be used in any setting. Identifiable information will not be reviewed by people outside of the clinical care team without consent. Posters will be provided to primary and secondary care sites to exhibit in appropriate areas so that patients may self-refer. These posters will also be customised for web-based display via the trial's unit, patient support groups and other relevant social media, and will contain contact details for the trial's unit, so that patients can be connected to a site local to them, if available. Participant Identification Centres (PIC) sites may also be used to help identify potential participants e.g. ambulatory services linked to a main site taking part in the trial. Patients will be invited to participate in either the main trial or the qualitative acceptability study, or both.

Potentially eligible patients will be invited to take part in the trial by their usual care team via post, text or email using the invitation letter and a PIS to provide further information about the trial.

Patients may be contacted by short message service (SMS) text message via their GP Practice or secondary care provider (standardised text to be used for text messages will be provided). This could be as a follow up to the participant invitation letter (sent in the post) or as an initial recruitment approach. Patients will be asked to contact their usual health care provider if they have any questions or are interested in taking part in the trial. Where it is an initial recruitment approach, patients will be provided with the PIS before the usual consent procedure is followed.

Once adequate time has been allowed to consider the trial, a screening appointment will be scheduled which will take place either at their usual GP practice, secondary care site, over the telephone or via an online video link.

6.2 Consent and Enrolment

A single consent process is being employed for STABILISE. Consent will cover screening and randomisation into the trial. This will reduce the number of required visits for patients. After extended consultation, we opted for the approach of screening and randomisation before the IGRA results as this would be more convenient for volunteers since it would require fewer visits. In addition, given the typical demographic of patients with COPD in the UK, and with the UK being a low endemic country for TB, we expect the rate of positive or indeterminate IGRAs to be extremely low. Therefore, the need to alter randomisation following a positive IGRA result is likely to be highly infrequent.

Screening investigations will be completed in-person with patients at their hospital, by delegated doctors, nurses, and research nurses. The informed consent process will be documented in the patient's medical records. An electronic Screening Form will be completed for all patients who are assessed for eligibility and will be used centrally to monitor recruitment. Each patient will be assigned a screening number in lieu of a trial number being allocated when they are randomised.

Baseline data will be collected via CRFs completed at this visit. This will include asking additional questions regarding existing and potential pregnancy. Data collected includes Participant details, medical history, concomitant medications (refer to Section 9 – Trial Procedures). These data will be ideally added to the trial EDC system by delegated site staff before randomisation but if this is not possible, then as soon afterwards as is feasible.

Spirometry will be performed to assess COPD severity, if it has not been performed in routine care; if it is available in the routine care record in the last 12 months that may be used instead. Where spirometry is performed it should be done whilst the patient is taking their usual inhalers. Demographic data, smoking status and degree of past smoke exposure (pack years), medical history and current medications will be collected. These data will be added to the trial EDC system by delegated site staff once eligibility is confirmed by the local investigator, or as soon as possible after randomisation. If the patient is not eligible, any completed assessments and worksheets will be destroyed in line with local confidential waste disposal protocols.

All patients will be asked to provide a blood sample (used to perform the IGRA test), DBS sample, a sputum sample and complete a nasopharyngeal (nose and throat) swab (if they produce in the stable state). Participants will also be taught how to obtain their own DBS sample by a medically qualified member of staff as they will be asked to complete this at home at the specified follow up time points. A patient interviewer-administered questionnaire will be used to collect quality of life (CAT score) and exacerbation management in the last 12 months.

6.3 IGRA test results

Only patients with a negative IGRA test result from the blood sample taken at baseline are eligible to join the trial. If a participant's result is indeterminate, the site should contact the patient to ask them to provide a new sample of blood for testing. If the result of the second IGRA test is indeterminate, the patient will be deemed as ineligible. If the participants result is positive, they should be referred for assessment of TB status. Once a negative IGRA result has been received, the participant is eligible to receive the vaccine if they are allocated to the intervention arm. It is anticipated that the results from the IGRA test to be available within 1-2 days with a maximum of a week. Eligibility will be affirmed by a medically trained doctor. Patients with positive or 2 indeterminate IGRA will be informed by a letter from their recruiting site that their blood test results didn't meet the study inclusion criteria.

6.4 Randomisation

Patients will be randomised after eligibility, excluding IGRA result, has been confirmed by a medically qualified doctor. Randomisation will be provided by the Birmingham Clinical Trials Unit (BCTU) using a secure online system (available at https://stabilise.bctu.bham.ac.uk), thereby ensuring allocation concealment.

Unique log-in usernames will be provided to those who wish to use the online EDC system and who have been delegated the role of randomising patients into the trial as detailed on the STABILISE site signature and delegation log. These unique log-in details must not be shared with other staff and in no circumstances should staff at sites access the system using another person's login details. The online trial EDC system will be available 24 hours a day, 7 days a week, apart from short periods of scheduled maintenance.

In the event of the online system not being available, a back-up telephone toll-free randomisation service ([name]) is available Monday to Friday, 09:00 to 17:00 UK time, except for bank holidays, government guided closures and University of Birmingham closed days.

6.5 Randomisation process

After informed consent has been given and participant eligibility, excluding IGRA result, has been confirmed, the participant can be randomised into the trial using the online EDC system. Worksheets will be provided to investigators and may be used to collate the necessary information prior to randomisation. All questions and data items on the online Randomisation Form must be answered appropriately prior to a potential participant being randomised into the trial and a Trial Number being issued.

Following randomisation, a confirmatory e-mail will be sent to the randomiser, local PI, local research nurse, trial mailbox, and the administrating site pharmacist. The local research nurse will inform participants of their allocation verbally.

The local research team should add the participant to the STABILISE Participant Recruitment and Identification Log which links participants with their trial number. The PI must maintain this document securely, which is not to be submitted to the Trial Office and should be held in strict confidence.

6.6 Randomisation method

Participants will be randomised at the level of the individual in a 1:1 ratio to either BCG vaccine or no vaccine via a central secure web-based EDC system. A minimisation algorithm will be used within the randomisation process to ensure balance in the BCG vaccine allocations over the following variables:

- Age (<65 or ≥65 years)
- Prior BCG vaccination or TB infection (yes/no)
- Consent to participate in the detailed mechanistic sub-study (yes/no)
- Site

To avoid the possibility of the intervention allocation becoming predictable, a random element will be included in the algorithm. Full details of the randomisation specification will be stored in a confidential document at BCTU.

6.7 Blinding

STABILISE is a PROBE trial and will utilise a Clinical Adjudication Committee (CAC) to assess the primary outcome to determine the number of exacerbations after randomisation using all available trial related clinical information. The adjudication committee will be blinded to the allocated treatment arm. They will look at basic patient details, symptoms of the AECOPD (from the patient), treatment history including any hospital admission (from the GP/medical record/CRF) and the laboratory test results (i.e. the sputum, swab and DBS samples).

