8. OUTCOME MEASURES

8.1 Internal pilot outcomes

An embedded internal pilot will run over a period of 9 months to assess site and participant recruitment and exclusion and primary outcome data completion.

The pilot outcomes are to:

Assess recruitment rate and exclusions: We aim for 20 sites enrolling at 9 months from study approval by the relevant authorities and target an overall recruitment rate of 1 patient per site per month. We will also examine reasons for non-inclusion of patients in the study; if high rates of exclusion occur due to patients declining, we will prioritise completion of qualitative acceptability work.

Assess primary outcome data completion: We aim for more than 90% of primary outcome data reported on the three month follow up form.

Assess an indication of the anticipated pooled AECOPD rate of the primary outcome: The pooled AECOPD rate at 3 months after date of treatment/randomisation will be used to indicate if the event rate is proceeding in line with what we would expect, such that the original sample size calculation remains accurate. The clinical adjudication committee will blindly review three-month AECOPD data collected directly from patients which will need confirmation via the routine care record (including data held on patient NHS App if necessary) at site, for the purposes of the 3-month review during the pilot. To meet the primary outcome of moderate to severe exacerbation, proof of antibiotic and/or steroid prescription (e.g. GP record of medication issue), and hospital admission (e.g. a discharge letter) respectively is required. Sites will be asked to confirm that such proof has been sent to be reviewed by the clinical adjudication committee.

We have considered Medical Research Council Hubs for Trials Methodology Research workshop guidance when determining stop/go criteria for the trial (43). Areas considered as suitable progression criteria include recruitment rate, protocol adherence (data completion) and outcome rate. A traffic

light system of green (go), amber (amend) and red (stop) was deemed preferable to a simple stop/go approach when specifying progression criteria for internal pilot studies, and they suggested recruitment progression criteria should be based on rates per centre per unit time that can be extrapolated, rather than specifying an absolute number by a specific date.

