8.2 Main trial outcomes

8.2.1 Primary outcome(s)

The primary outcome is moderate to severe AECOPD rate over 12 months follow up from IMP administration date (or from the date of randomisation if no treatment was administered). This is defined by the clinical adjudication committee and will be based on an assessment of:

- basic patient details
- healthcare utilisation (taking additional antibiotics and/or steroids, as recorded in the medical record, including prescription data),
- patient-reported symptoms of the AECOPD
- laboratory results from patient-provided sputum, saliva, nose/throat swabs and DBS samples following an exacerbation

Severe events are defined by additional hospitalisation. Confirmation of events as stated in section 8.1, will occur via the CAC. Terms of reference for the CAC will be set.

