9.5 Follow up visits – One month and three months (mechanistic sub-group only)

If a participant has agreed to take part in the mechanistic sub-group, visits to their local research site will be arranged by the site at one and three months from the date the participant's BCG was administered for those in the intervention arm or from the date of randomisation for those in the control arm. Site staff will take additional blood samples from participants at these visits. During the three-month visit, questionnaires will be completed as for all other patients and DBS test performed. The DBS test will be sent to the main laboratory based at the QE hospital.

Data point to be collected:

- Venepuncture
- DBS
- Exacerbations since baseline
- Hospitalisations
- CAT test

9.6 Three month follow up visit (participants not taking part in the mechanistic sub-group)

Participants will be sent a link via email or SMS text message to access and complete their three month follow up questionnaire at home (paper copies can be posted if requested). This is sent to the participant automatically by the trial EDC system. Participants will also complete a DBS test at home and post the sample to the main laboratory based at the QE hospital. If a participant does not complete the questionnaire online after being sent the link three times on days 2, 3 and 5 from the missed due date, the trial team will send the questionnaire via post (paper) to the participant 7 days from the missed due date. The participant will be asked to complete and return the questionnaire to the trial team at BCTU, in the format it was received. If no response is received/completed after the attempts have been made, this data will be considered missing for this follow up time point.

Data point to be collected:

- DBS
- Exacerbations since baseline
- Hospitalisations
- CAT test

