14.2.1 Primary estimand

The primary estimand is the rate of moderate to severe acute exacerbations of AECOPD in adults with a primary clinical diagnosis of COPD and will be measured as the rate per person per year. The estimand will follow the principal stratum strategy and those who will be randomised and then receive a positive or indeterminate result in their IGRA test will be excluded from all analyses.

The primary estimand can be summarised as follows:

Population: Adults with a primary clinical diagnosis of COPD and a negative IGRA test, ≥2 AECOPD in the last 12 months, who have not been Immunosuppressed and have not received >20mg prednisolone per day for >14 days in the last 3 months, have not previously experienced of allergic reaction to vaccine and are not pregnant, if they are female.

Treatment Conditions: BCG vaccine compared to no vaccine (see Section 7.1 for details on the intervention)

Outcome: Rate per person per year of moderate to severe acute exacerbations of AECOPD

Time: 12 months after randomisation in the no vaccine group and 12 months after receiving the BCG vaccine in the BCG group

Summary Measure: Adjusted incidence rate ratio and 95% confidence interval

Intercurrent Events and Strategies: The intercurrent events are: positive or indeterminate IGRA test; treatment non-receivers (those who randomised to receive but did not receive the BCG vaccine for any reason); withdraw consent for providing follow up data or lost to follow up; and death. All intercurrent events apart the first one (i.e. tested positive in their IGRA test) will be dealt with using the treatment policy strategy for the primary estimand as we want to evaluate the treatment effect as it would occur in normal practice. The intercurrent event, positive or indeterminate IGRA test will be dealt with using the principal stratum strategy because we are interested in the treatment effect in the principal stratum in which the intercurrent event would not occur.

Other strategies evaluating different estimands will be discussed in further detail in the SAP.

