Rate of moderate to severe acute exacerbations of AECOPD will be analysed using a negativebinomial regression model, incorporating exposure time (person-years) and adjusting for the minimisation variables listed in Section 6.6 to estimate the adjusted incidence rate ratio and 95% confidence interval. The two-sided p-value relating to the intervention group parameter as generated by the model will be presented.

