18.7 Clinical Adjudication Committee (CAC)

The Clinical Adjudication Committee will review the relevant medical history and trial data for each of the participants recruited into the trial to determine the incidence of COPD exacerbation within the patient cohort. The CAC will not be aware of the treatment allocation of the trial participants and trial data will be supplied in confidence by the trial office. The CAC's determination of the incidence of COPD exacerbation will serve as the primary outcome data for the trial.

The CAC will operate in accordance with the trial CAC Charter which will define the membership, roles, and responsibilities. The CAC will meet every three months with additional meetings arranged during periods when the volume of recruitment is higher than expected.

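### The protocol gives conflicting start dates for counting primary-outcome events in the BCG arm: randomisation or baseline in some sections, vaccination in others

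*Protocol*

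**What the plan says.** **Sections that start at randomisation or baseline**

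- Protocol 6.7 gives the CAC's task as "to determine the number of exacerbations after randomisation using all available trial related clinical information", with no distinction by arm. The committee is blinded to allocation.
- Protocol 18.7: "The CAC's determination of the incidence of COPD exacerbation will serve as the primary outcome data for the trial".
- Protocol 9.5 and 9.6 list "Exacerbations since baseline" among the three-month data. Randomisation takes place at the baseline visit (9.2, 9.8), so baseline and randomisation are in effect the same date.

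**Sections that start at vaccination in the BCG arm**

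- Protocol 8.2.1: "The primary outcome is moderate to severe AECOPD rate over 12 months follow up from IMP administration date", or from randomisation where no vaccine was given.
- Protocol 14.2.1, time attribute of the estimand: "12 months after randomisation in the no vaccine group and 12 months after receiving the BCG vaccine in the BCG group".
- Protocol 9.8, footnote 2, sets the follow-up dates by the same arm-specific clock.
- Protocol 8.1: "The pooled AECOPD rate at 3 months after date of treatment/randomisation will be used to indicate if the event rate is proceeding" in line with expectation.

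**Link between the two.** Protocol 7.1 allows up to 6 weeks from randomisation to vaccination. The primary model is described as "incorporating exposure time (person-years) and adjusting for the minimisation variables", and that sentence does not say when the person-years begin.

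**The concern.** In controls the two start dates coincide. In vaccinated BCG participants they differ by the delay to vaccination. Some delay is built into the design: 6.3 requires a negative IGRA result first, and 7.1 batches vaccination from multi-dose vials through shared hubs.

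Take a BCG participant who has a treated exacerbation in week 3 and is vaccinated in week 6. Under 6.7 the event belongs to the count; under 8.2.1 and 14.2.1 it does not. No section says who removes it. The CAC cannot apply an arm-dependent start date and stay blinded.

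The collection windows repeat the mismatch. The three-month form runs from baseline to three months after vaccination, and the twelve-month form (9.7) asks about exacerbations over the last 9 months. Together they span 12 months in controls, but 12 months plus the delay in vaccinated BCG participants. The hospitalisation item in 9.7 looks back 12 months and does match the outcome window.

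If the wider count met the narrower person-time, the bias would run against BCG. The pooled three-month rate would be too high, and 2.1 and 8.1 use that rate to judge whether the sample size still holds.

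**Working it through.** **Inputs.** Rates of 2.25 (control) and 1.8 (BCG) per person-year, two-sided 5% type 1 error, 90% power and 361 per group (14.1, 14.2); dispersion k = 0.36 (14.1); maximum delay 6 weeks (7.1). The protocol gives no mean delay, so the delay w is an assumption.

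**1. The plan's own figure.** Two-rate negative binomial formula, one year of exposure, null variance from the pooled rate (2.25 + 1.8)/2 = 2.025:

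- V0 = 2/2.025 + 2 × 0.36 = 1.708
- V1 = 1/2.25 + 1/1.8 + 2 × 0.36 = 1.720
- n = [1.960 × √1.708 + 1.282 × √1.720]² / (ln 0.80)² = 361.4 per group, agreeing with the stated 361
- 361/0.9 = 401.1, rounded up to 402, as stated

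**2. One window for events and person-time, starting at vaccination.** The rate ratio is 1.8/2.25 = 0.80. There is no inflation and power stays at 90%.

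**3. Events from randomisation, person-time from vaccination.** Assume a pre-vaccine rate of 2.25 per year and the same delay of w weeks for every BCG participant.

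- Extra BCG events per person = 2.25 × w/52, with no added person-time
- Apparent BCG rate R = 1.8 + 2.25 × w/52; apparent rate ratio = R/2.25
- Power = Φ(|ln(R/2.25)|/SE − 1.960), with SE = √[(1/2.25 + 1/R + 0.72)/361]
- Pooled three-month rate, annualised = (2.25 × 0.25 + 1.8 × 0.25 + 2.25 × w/52)/0.5

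| Delay w (weeks) | Extra events | BCG rate | Rate ratio | Power | Rate ratio if no true effect | Pooled pilot rate |
|---|---|---|---|---|---|---|
| 0 | 0 | 1.800 | 0.800 | 90% | 1.000 | 2.025 |
| 1 | 0.043 | 1.843 | 0.819 | 83% | 1.019 | 2.112 |
| 2 | 0.087 | 1.887 | 0.838 | 73% | 1.038 | 2.198 |
| 3 | 0.130 | 1.930 | 0.858 | 61% | 1.058 | 2.285 |
| 4 | 0.173 | 1.973 | 0.877 | 49% | 1.077 | 2.371 |
| 6 | 0.260 | 2.060 | 0.915 | 26% | 1.115 | 2.544 |

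Example, w = 3: R = 1.8 + 0.130 = 1.930; ln(1.930/2.25) = −0.1535; SE = √[(0.444 + 0.518 + 0.72)/361] = 0.0683; 0.1535/0.0683 − 1.960 = 0.29; power 61%.

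The pooled pilot rate is 13% too high at 3 weeks (2.285/2.025) and 26% too high at 6 weeks (2.544/2.025).

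**4. One window, starting at randomisation for 12 months in both arms.** The rate ratio is [2.25 × w/52 + 1.8 × (1 − w/52)]/2.25, which is 0.81 at 3 weeks and 0.82 at 6 weeks. Most of the distortion in step 3 therefore comes from the mismatch, not from which start date is chosen.

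**The case against.** The strongest reply is that 8.2.1 and 14.2.1 define the rate itself, and a rate over a stated window fixes both its events and its person-time. On that reading a pre-vaccine event is outside the outcome by definition, and 8.1 already gives the pilot rate an arm-specific start. The phrase in 6.7 sits in a blinding section and may only separate on-trial events from history. The entries in 9.5 and 9.6 are lists of data to collect, and collecting a wider period than is analysed is no error. Dated evidence should exist: an exacerbation form completed at the event (11.2), and prescriptions or discharge letters (8.1). The trial office or statistician could then apply the window without unblinding the CAC, and the SAP, which is not at hand, may say so. Event rate is also absent from the traffic-light criteria in Table 1.

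Much of this stands. A reader might infer that the planned analysis counts BCG events from randomisation and divides by person-time from vaccination, so that the trial is underpowered as designed. The documents do not support that. No section tells the analyst to combine the two, and the model description gives no start date for person-years. BCG participants who are never vaccinated start at randomisation under 8.2.1 and would be unaffected.

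What the reply does not remove is the contradiction. The instruction to the CAC, its status as the source of primary outcome data, and the recall period of the form are protocol text, and they do not match the outcome definition. No one is assigned to filter. Although event rate is not a traffic-light criterion, 2.1 allows a sample size adjustment based on the three-month rate.

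**Conclusion.** The concern holds as a contradiction in the counting window for the primary outcome. Sections 6.7, 18.7, 9.5 and 9.6 point to randomisation or baseline; 8.1, 8.2.1, 9.8 and 14.2.1 point to vaccination in the BCG arm. Following the second group for both events and person-years leaves no bias of this kind.

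The table gives the size only if unfiltered counts meet person-time from vaccination. It rests on a common delay for all BCG participants, a pre-vaccine rate of 2.25 per year, everyone in the BCG arm vaccinated, and 361 per arm with a full year of follow-up. The 6-week row puts everyone at the permitted maximum. The figures show why the wording should be settled; they do not predict the trial's power.

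Reconciling on vaccination leaves a separate matter: the start date would still differ between the arms, and events between randomisation and vaccination would be dropped in the BCG arm only.

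**What to change.** - Reconcile 6.7, 9.5, 9.6 and 18.7 with 8.1, 8.2.1, 9.8 and 14.2.1 so that events and person-years share one start date within each arm. State that date beside the person-years term in 14.2.1. The match is needed whichever start date is kept.
- In 6.7, 18.7 and the CAC form, require an onset date for every confirmed event.
- Have the trial statistician, not the blinded CAC, count only events with onset inside the interval used for the person-years offset.
- Apply the same rule to the pooled three-month pilot rate.
- In 9.5 and 9.6, either ask about exacerbations since the participant's follow-up start date, pre-filled by the data capture system, or keep the wider question and state that the date filter applies.

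Cost: wording in a few sections and the CAC form, plus one date filter in the analysis program. No extra participants or visits are needed.
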